6.2.4. Clinical laboratory sampling

Non-fasting samples for clinical laboratory analysis will be collected by a qualified staff member at Visit 1, at Visit 2 prior to randomization and at Visit 9. The following tests, at a minimum, will be conducted:

Chemistry Panel	Complete Blood Count
Albumin	Hematocrit
Alkaline phosphatase	Hemoglobin
Alanine aminotransferase (ALT)	Platelet count
Aspartate aminotransferase (AST)	Red blood cell morphology
Blood urea nitrogen (BUN)	Red blood cell count
Bicarbonate	White blood cell count
Calcium	White blood cell differential
Chloride	% & absolute
Creatinine	Basophils
Glucose	Eosinophils
Lactate dehydrogenase (LDH)	Lymphocytes
Phosphorus	Monocytes
Potassium	Neutrophils
Sodium	
Total bilirubin	
Total protein	
Uric acid	

The results of the clinical laboratory tests will be reported on the laboratory's standard reports. The investigator must note NCR or CR to define the clinical relevance of any result that is outside the normal range for the laboratory. The investigator must date and initial every laboratory report.

The investigator must review the subjects' Visit 1 laboratory reports prior to Visit 2. The subject must not be randomized at Visit 2 if any of the Visit 1 results are outside normal range for the laboratory AND, in the opinion of the investigator, CR.

The investigator must review all laboratory reports in a timely manner

The investigator must report all laboratory results that are BOTH outside the normal range for the laboratory AND, in the opinion of the investigator, CR as medical history if found prior to the first study medication application or as an AE if found after the first study medication application begins (Section 7.1).

6.2.5. Urine pregnancy tests

The investigator or designee will perform a urine pregnancy test for subjects who are WOCBP (Section 8) at Visit 1, at Visit 2 prior to randomization and at Visit 9. The urine pregnancy test kits used must have a minimum sensitivity of 25-mIU β -HCG/milliliter (mL) of urine.

Subjects who are WOCBP must have a negative pregnancy test result at Visit 1 to be enrolled and at Visit 2 to be randomized.

If the result of any post-randomization urine pregnancy test is positive, the subject will be withdrawn from the study and the subject's pregnancy documented and followed (Section 8).

6.3. Other Evaluations

6.3.1. Demographics and medical history

At Visit 1, the investigator or designee will interview each subject to obtain demographic information including date of birth, sex at birth, skin type, race and, if appropriate, ethnicity.

Medical history information will be recorded including all medical conditions, all disease states that require concomitant therapy and other medical conditions and disease states that, in the opinion of the investigator, are relevant to the subject's study participation.

6.3.2. Standardized photography

At every study visit standardized color photographs of each target lesion will be taken. At Visit 2, and if appropriate Visit 5, the photographs must be taken prior to the study medication application.

Care must be taken to ensure the same lighting, background, subject positioning relative to the camera and camera settings are used for each photograph. Equipment, supplies and detailed instructions for obtaining and managing the photographs will be provided to the investigational center prior to the initiation of subject enrollment.

The photographs are to document the appearance of the subjects' target lesions.

At Visit 1, photographs will be taken as part of the target lesion identification (Section 5.4).

7. ADVERSE EVENTS

Adverse events will be monitored throughout the study and immediately reported on the appropriate Aclaris Therapeutics, Inc. AE CRF.

7.1. Definitions

7.1.1. Adverse events (AE)

An AE is any untoward medical occurrence in a patient or clinical investigation subject administered a study medication(s) and which does not necessarily have a causal relationship with the study medication. An AE can therefore be any unfavorable and unintended sign or symptom associated with the use of a study medication (including an abnormal laboratory finding), whether or not related to the study medication.

Thus any new, clinically relevant worsening of an existing sign, symptom or disease, should be considered an AE.

Except for Local Skin Reactions, (see below) worsening of any of the target lesion assessments must be reported as an AE ONLY if the use of the study medication is interrupted or discontinued or if therapy is required to manage the event. Any LSR that increases in severity, compared to the Visit 2 pre-application evaluation, by ≥ 1 grade AND persists for 2 or more successive visits must be reported as an AE.

The investigator must report the target lesion number(s) for any AE associated with a target lesion and should question the subject in detail to determine if there are any confounding factors (e.g., irritation by clothing or activity, sunburn) for any such AE.

Every new episode or clinically relevant worsening of a chronic condition (e.g., headaches, seasonal allergies, depression, and hypertension) should be reported as a separate AE, even if the condition is reported in the subject's medical history.

The investigator should, when certain, report a diagnosis rather than the signs, symptoms or clinically relevant abnormal laboratory values associated with the AE. Otherwise, signs, symptoms or abnormal laboratory values may be used to describe the AE.

Any CR abnormality discovered prior to the first study medication application should be reported as medical history, not as an AE.

7.1.2. Serious adverse event (SAE)

A Serious Adverse Event is any untoward medical occurrence that at any dose:

- Results in death
- Is life threatening
- Requires inpatient hospitalization or prolongation of existing hospitalization
- Results in persistent or significant disability/incapacity, or
- Is a congenital anomaly/birth defect
- Is an important medical event.

The term “life threatening” refers to an event in which the subject was at risk of death at the time of event; it does not refer to an event that hypothetically might have caused death if it was more severe.

Inpatient hospitalization is considered to have occurred if the subject is admitted to the hospital on an in-patient basis, even if released the same day. Prolongation of hospitalization is defined as an additional night stay in the hospital. Hospitalization for a diagnostic test (even if related to an AE) or elective hospitalization that was planned before study enrollment (signing the ICF) are not themselves reasons for an event to be defined as a SAE.

Important medical events are those that may not be immediately life threatening, result in death or hospitalization, but are clearly of major clinical significance and may jeopardize the subject or require intervention to prevent one of the outcomes listed in the SAE definition above. These should also usually be considered serious. Examples of such events are intensive treatment in an emergency room or at home for allergic bronchospasm, blood dyscrasia or convulsions that do not result in hospitalization.

7.1.3. Unexpected adverse event

An AE is considered unexpected if it is not listed in the Investigator Brochure or is not listed at the specificity or severity that has been observed.

7.1.4. Adverse event reporting period

Non-serious AEs must be reported starting when the subject performs the first study medication application until the end of the subject’s last study visit. SAEs must be reported starting when the subject signs the ICF until the end of the subject’s last visit.

7.1.5. Severity

The investigator is to define the severity each AE using the following definitions as a guideline. The investigator will consider the range of the possible severity of the event and identify the severity that is the most appropriate according her/his medical judgment.

Mild – Awareness of signs or symptom, but easily tolerated

Moderate – Discomfort, enough to cause interference with usual activity

Severe – Incapacitating with inability to perform usual activity.

7.1.6. Relationship to study medication

The investigator will determine if there is a reasonable causal relationship between the study medication and an AE or not. The investigator will use her/his best medical judgment and consider all relevant factors (*e.g.*, temporal relationship, location of the event, the subject's relevant medical history, concomitant therapies and concurrent conditions) to determine the relationship of the AE to the study medication. The investigator will define the relationship of an AE to the study medication by selecting one of the following categories:

Related – There is a reasonable possibility that there is a causal relationship between the study medication and the AE.

Not Related – There is not a reasonable possibility that there is a causal relationship between the study medication and the AE.

The term “reasonable causal relationship” means there are facts or arguments to suggest a causal relationship (International Conference on Harmonization (ICH) E2A).

7.2. Reporting Procedures

7.2.1. Procedures for reporting adverse events

At each post enrollment visit, the investigator will question the subject to elicit AEs using a non-directive question such as “Has there been any change in your health since the previous study visit?” The investigator will also question the subject in the same manner to elicit AEs during visits when study medication applications are conducted.

If appropriate, based on the subject's response, directed follow-up questions and appropriate evaluations should be conducted.

Any AE noted during the reporting period (Section [7.1.4](#)) must be reported in the source documents and on the appropriate AE CRF.

AEs that are defined as “Not Related” to the study medications will be followed until they are resolved or until the subject’s last study visit. AEs that are defined as “Related” to the study medications will be followed until they are resolved or, if not resolved after the subject’s last study visit, until in the opinion of the investigator, the AE reaches a clinically stable outcome with or without sequelae.

7.2.2. Procedure for reporting a serious adverse event

Upon becoming aware of a SAE occurring during the AE reporting period, whether or not related to the study medications, the investigator must:

1. Take the appropriate medical action to ensure the subject’s safety
2. Immediately inform the Medical Monitor of the SAE by telephone:

[name].
Aclaris Therapeutics, Inc.
[name]
[name]
[name]
Office [contact]
Mobile [contact]
SAE [contact]
E-mail: [contact]

3. Within 24-hours complete, as fully as possible, an AE CRF and an SAE form; fax or e-mail the forms and any other relevant information (*e.g.*, concomitant medication CRF, medical history CRF, laboratory test results) to the Aclaris Therapeutics, Inc. Medical Monitor.
4. Monitor and document the progress of the SAE until it resolves or, if not resolved after the subject’s last study visit, until in the opinion of the investigator the AE reaches a clinically stable outcome with or without sequelae AND the investigator and Aclaris Therapeutics, Inc. Medical Monitor agree that the SAE is satisfactorily resolved.
5. Inform the Aclaris Therapeutics, Inc. Medical Monitor of SAE updates by telephone followed by an SAE form update sent by fax or by e-mail.
6. Comply with the appropriate regulatory requirements and Aclaris Therapeutics, Inc. instructions regarding reporting of the SAE to the responsible Institutional Review Board (IRB) or Ethics Committee (EC).

8. PREGNANCY

WOCBP include any female who has experienced menarche and who has not undergone successful surgical sterilization (hysterectomy, bilateral tubal ligation or bilateral oophorectomy) or is not postmenopausal (defined as ≥ 12 months with no menses without an alternative medical cause). Women who are using an active method of birth control, are practicing abstinence, or where the partner is sterile (*e.g.*, vasectomy), should be considered to be WOCBP.

All WOCBP must use an effective method of birth control during the course of the study, in a manner such that risk of failure is minimized. Effective methods of birth control approved for use in this study are:

- Implants
- Injectables
- Patch
- Combined oral contraceptives
- ParaGard® or Mirena® intrauterine devices
- Condom with spermicide; diaphragm with spermicide
- Vasectomized partner.

Prior to trial enrollment, WOCBP must be advised of the importance of avoiding pregnancy during trial participation and the potential risk factors for a pregnancy. The subject must sign an informed consent form documenting this discussion. During the trial all WOCBP will be instructed to contact the investigator immediately if they suspect they might be pregnant (*e.g.*, missed or late menstrual period).

If a subject or investigator suspects that the subject may be pregnant prior to study medication administration, the study medication must be withheld until the results of a pregnancy test are available. If pregnancy is confirmed, the subject must not receive study medication and must be discharged from the study.

If, following study medication administration, it is determined that the subject may have been or was pregnant at the time of study medication exposure (including at least 2 days after study medication administration) the investigator must immediately notify the Aclaris Therapeutics, Inc. Medical Monitor and record the event on a pregnancy surveillance form. While not an AE or SAE, every pregnancy must be reported using a pregnancy surveillance form and follow the reporting procedures described for SAE reporting (Section [7.2.2](#)).

Protocol-required procedures for trial discontinuation and follow-up must be performed on the subject unless contraindicated by pregnancy (*e.g.*, x-ray studies). Other appropriate pregnancy follow-up procedures should be considered if indicated. In addition, the investigator must report to Aclaris Therapeutics, Inc.'s Medical Monitor on the pregnancy surveillance form, follow-up information regarding the course of the pregnancy, including perinatal and neonatal outcome. Infants should be followed for a minimum of six weeks.

9. STATISTICAL ANALYSES

9.1. Statistical Analysis of Clinical Indices

The primary effectiveness analyses will be pairwise comparisons between Vehicle and each active study medication, based on mean change from Visit 2 PLA, using a repeated-measures Analysis of Covariance model suitable for the study design. Study medication concentration is the within-subject independent variable. The Visit 2 score will be the covariate. The primary analysis visit will be Visit 9. An exploratory dose-response analysis may be conducted across concentrations to evaluate a concentration trend, as well as an exploratory longitudinal analysis across visits to evaluate trends over time.

Secondary efficacy analyses will include a similar analysis of SSA, SSK and other evaluations suitable for analysis as continuous variables. Separate primary and secondary effectiveness analyses at each post-baseline visit will be conducted. In addition, secondary analyses will be performed on proportion of PLA and SSA responders, where a subject will be considered a responder if the Visit 9 score is 0. A similar analysis will be done at Visit 5. Chi-square will be used to analyze differences in response rates under the assumption that lesions within a subject may be treated independently, along with a repeated-measures logistic regression model applied as an optional exploratory analysis method.

For all analyses two-tail alpha will be set at 0.05 with no adjustment for multiplicity due to the exploratory nature of the study. The Intent-to-Treat (ITT) population, defined as subjects with data for both Visit 2 and at least one post-Visit 2, will be the primary analysis population, supplanted by analyses of the Per-Protocol (PP) population defined as ITT subjects with no missing effectiveness data and no major protocol violations. ITT population analyses will use last-observation-carried-forward to impute missing post-Visit 2 data.

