1. SYNOPSIS

Title:

A Randomized, Double-Blind, Vehicle-Controlled, Within Subject Comparison Study of the Safety, Tolerability and Effectiveness of A-101 Topical Solution in Subjects with Seborrheic Keratosis.

Objectives:

The main objective of this study is to evaluate the safety and effectiveness of A-101 (hydrogen peroxide) Solution 25%, 32.5% and 40% when applied to individual seborrheic keratosis (SK) target lesions on the back compared with a matching A-101 Solution Vehicle.

Methodology/Study Design:

The duration of study participation is anticipated to be a maximum of 95 days per subject. This includes the up to 14-day screening period, a visit for a required study medication application, a 21-day no treatment period, a visit for an optional study medication retreatment application, a 56-day no treatment follow-up period and a maximum allowable 4-day Visit 9 visit window. Study visits are:

- Visit 1 (Day -13 to 0) enrollment; start screening period
- Visit 2 (Day 1) randomization; study medication application
- Visit 3 (Day 8) no treatment follow-up
- Visit 4 (Day 15) no treatment follow-up
- Visit 5 (Day 22) follow-up visit where target lesions that meets the retreatment criteria will receive a second study medication application
- Visit 6 (Day 29) no treatment follow-up
- Visit 7 (Day 43) no treatment follow-up
- Visit 8 (Day 57) no treatment follow-up
- Visit 9 (Day 78) no treatment follow-up; end of study.

During Visit 1 the investigator will, for each subject, identify 4 individual SK lesions (target lesions) on the back for treatment, perform an electrocardiogram (ECG) and collect blood samples for clinical laboratory safety tests to determine the subject's eligibility for randomization. Subjects may have more than 4 SK lesions on the back, or on other body surfaces, but only the target lesions on the back will be evaluated and treated.

During Visit 2, eligible subject's target lesions will be randomized, each to receive 1 study medication (a unique study medication for each target lesion) and then the study medication applications will be performed. Every eligible subject will receive all 4 of the study medications.

At Visits 3 and 4, subjects will be seen for a no treatment follow-up.

At Visit 5, subjects will be seen for follow-up and any target lesion that meets the re-treatment criteria (*i.e.*, Physician's Lesion Assessment [PLA] >0) will receive a second study medication application.

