The investigator will evaluate Signs of Seborrheic Keratosis (SSK) throughout the study and take standardized color photographs to document the status of the target lesions throughout the study.

Statistical Methods:

The primary effectiveness analyses will be comparisons between Vehicle and each active treatment, based on mean change from the Visit 2 PLA, using a repeated-measures Analysis of Covariance model suitable for the study design. For this purpose, the primary analysis visit will be Visit 9. Secondary effectiveness analyses will include a similar analysis of SSA and other effectiveness evaluations suitable for analysis as continuous variables. In addition, secondary analyses will be performed on proportion of PLA and SSA responders, where a subject will be considered a responder if the Visit 9 score is 0. A similar responder analysis will be done at Visit 5. Chi-square will be used to analyze difference in response rates.

LIST OF ABBREVIATIONS AND DEFINITIONS OF TERMS

Abbreviation	Term
AE	Adverse Event
°C	Degrees Centigrade
cm	Centimeters
CR	Clinically Relevant
CRA	Clinical Research Associate
CRF	Case Report Form
CRO	Contract Research Organization
e.g.	for example (Latin; exempla gratia)
EC	Ethics Committee
ECG	Electrocardiogram
°F	Degrees Fahrenheit
FDA	Food and Drug Administration
g	Gram
GCP	Good Clinical Practice
HIPAA	Health Insurance Portability and Accountability Act of 1996
IB	Investigator's Brochure
ICF	Informed Consent Form
ICH	International Conference on Harmonization
i.e.	that is (Latin; id est)
IPL	Intense Pulsed Laser
IRB	Institutional Review Board
ITT	Intent To Treat
LSR	Local Skin Reactions
MedDRA	Medical Dictionary for Regulatory Activities
mL	Milliliter
NCR	Not Clinically Relevant
OTC	Over-The-Counter
PDT	Photodynamic Therapy
PLA	Physician's Lesion Assessment
PP	Per Protocol
SAE	Serious Adverse Event

Abbreviation	Term
SK	Seborrheic Keratosis
SN	Subject Number
SOP	Standard Operation Procedure
SSA	Subject's Self-Assessment
SSK	Signs of Seborrheic Keratosis
US	United States
WOCBP	Women of childbearing potential

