9.3. Sample Size

The sample size of 32 subjects completing this study was based on the estimated primary efficacy variable response rates for the most effective active medication and vehicle, which are expected to be approximately 60% and 10% respectively. This difference is expected to yield approximately 88% power using a standard chi-square test under the assumption of lesion independence.

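### The PLA and SSA responder rates of matched lesions are compared with an independent-groups chi-square, and the only within-subject responder method is optional

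*Combined protocol and SAP*

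**What the plan says.** The synopsis of the combined protocol and SAP sets out a fully within-subject design: "Every eligible subject will receive all 4 of the study medications". Section 9.1 carries this into the primary analysis, a repeated-measures ANCOVA of change in PLA: "Study medication concentration is the within-subject independent variable".

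The secondary responder analyses (PLA and SSA at Visit 9, and similarly at Visit 5) are handled differently. Section 9.1 says "Chi-square will be used to analyze differences in response rates under the assumption that lesions within a subject may be treated independently", and adds "a repeated-measures logistic regression model applied as an optional exploratory analysis method". The synopsis mentions only the chi-square: "Chi-square will be used to analyze difference in response rates".

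The responder is described at subject level, "where a subject will be considered a responder if the Visit 9 score is 0", although each subject contributes four lesion scores.

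On error control, section 9.1 says: "For all analyses two-tail alpha will be set at 0.05 with no adjustment for multiplicity due to the exploratory nature of the study". Section 9.3 gives the expected response rates for the most effective active medication and vehicle, "which are expected to be approximately 60% and 10% respectively", and also assumes independent lesions. No within-subject correlation is given anywhere.

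**The concern.** The design produces matched pairs, and the responder test ignores the matching. The plan declares the independence assumption but does not support it. Lesions on one back share the subject's skin and the same assessor (section 6) and, for the SSA, the same self-rater. Some positive correlation is therefore plausible, though its size is unknown.

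The variance used by the independent-groups chi-square leaves out the covariance between paired lesions. With positive correlation the standard error is too large, so the true level falls below 5% and the test gives up power that the design offers. With negative correlation, which nothing in the documents suggests, the error would go the other way.

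What is at stake is the comparison of less effective concentrations with vehicle. Three concentrations are tested, and the 60% planning rate applies only to the best one. Leaving the within-subject model optional also allows the responder method to be settled after the results are known.

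**Working it through.** **Inputs from the documents.** 32 completing subjects, hence 32 matched pairs per active-versus-vehicle comparison (sections 4.1 and 9.3); two-sided 0.05 without multiplicity adjustment (9.1); 60% versus 10% (9.3).

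**Assumed.** The within-subject correlation phi between two lesions' binary responses; rates other than 60% and 10%; chi-square read as an uncorrected 2×2 test of each active against vehicle. Section 9.1 names pairwise comparisons only for the primary analysis.

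**The plan's own figure.** Section 9.3 states about 88% power for an independent-groups chi-square. With the pooled-variance normal approximation,

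power = Φ{[|p1 − p2|√n − 1.96√(2p̄(1 − p̄))] / √(p1(1 − p1) + p2(1 − p2))}, p̄ = 0.35:

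- n = 16 per group: (2.000 − 1.322)/0.574 = 1.18, power 88.1%.
- n = 32 per group: (2.828 − 1.322)/0.574 = 2.62, power 99.6%.

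So 88% corresponds to 16 lesions per medication, while the design supplies 32. That is a separate matter. Here it shows only that the planned contrast has ample power under either test.

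**Joint distribution of a pair.** P(both respond) = p1·p2 + phi·√(p1(1 − p1)p2(1 − p2)); the other three cells follow from the margins. P(both respond) cannot exceed the smaller margin, which caps phi:

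- 60% versus 10%: (0.10 − 0.06)/√(0.6·0.4·0.1·0.9) = 0.04/0.147 = 0.27.
- 35% versus 10%: (0.10 − 0.035)/√(0.35·0.65·0.1·0.9) = 0.065/0.143 = 0.45.

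**Method.** All paired tables with n = 32 were enumerated and their multinomial probabilities summed where |z| > 1.96, for the uncorrected chi-square and for asymptotic McNemar, z = (b − c)/√(b + c), with b and c the two discordant counts.

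**True level, both rates 30%:**

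| phi | Chi-square | McNemar |
|---|---|---|
| −0.1 | 6.3% | 4.7% |
| 0 | 5.2% | 4.5% |
| 0.2 | 3.0% | 4.3% |
| 0.3 | 2.1% | 4.3% |
| 0.5 | 0.7% | 4.7% |

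As a rough check, under the null the chi-square standard error is too large by 1/√(1 − phi). At phi 0.3 this is 1.195, so the effective cut-off is 1.96 × 1.195 = 2.34, a level of about 1.9%; enumeration gives 2.1%. At rates of 10%, 30% and 50% with phi from −0.1 to 0.5, chi-square ranges from 0.7% to 7.3% and McNemar from 2.9% to 5.1%.

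**Power, chi-square / McNemar:**

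| Rates | phi 0 | phi 0.1 | phi 0.2 | phi 0.3 |
|---|---|---|---|---|
| 60% vs 10% | 99.6 / 99.4 | 99.7 / 99.8 | 99.9 / 99.9 or more | not feasible |
| 50% vs 10% | 96.2 / 95.2 | 97.0 / 97.0 | 97.8 / 98.6 | 98.6 / 99.8 |
| 40% vs 10% | 82.8 / 79.6 | 84.1 / 83.7 | 85.5 / 88.4 | 87.2 / 93.5 |
| 35% vs 10% | 69.8 / 65.7 | 70.8 / 70.4 | 71.8 / 76.0 | 73.1 / 82.9 |
| 30% vs 10% | 53.3 / 49.0 | 53.4 / 53.2 | 53.6 / 58.7 | 53.7 / 65.7 |

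The two tests break even near phi 0.1.

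**Other paired methods.**

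- Exact McNemar: 56% power at 35% versus 10%, phi 0, against 66% for the asymptotic version.
- Mid-p McNemar: level 2.2% at 10% rates and phi 0.2, against 4.7% for asymptotic McNemar and 3.3% for chi-square.
- Logistic model (200,000 simulated trials; two-arm marginal log-odds Wald test; uncorrected robust variance; non-estimable trials counted as non-rejections; phi 0 to 0.5): level 1.2–2.0% at 10% rates, 4.9–5.5% at 30% and 5.6–7.0% at 50%.
- Chance of no vehicle responder among 32: 0.9³² = 3.4% at a 10% rate, 0.95³² = 19% at 5%.

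**The case against.** The plan discloses the assumption, names a within-subject model beside it, calls the study exploratory, and keeps the matching in its primary analysis. Under positive correlation the error is on the safe side, and at the only rates the documents give the choice of test does not matter. The benefit depends on two things they do not give: a correlation above about 0.1 and a modest difference. At phi 0.2 the gain over chi-square against a 10% vehicle rate shrinks from 4.2 points at 35% to 2.9 at 40% and 0.8 at 50%. If lesions are truly independent, McNemar loses about 4 points. Mid-p McNemar is nearly as powerful as the asymptotic version at 35% and 30% versus 10%, at most 2.4 points lower for phi 0.2 to 0.3.

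Most of this stands and limits the weight of the point. It does not remove it. Disclosing an assumption does not make the error rate right when the assumption fails, and an optional model does not commit the analysis to anything. Part of the 4-point loss reflects chi-square's slightly higher true level at phi 0 (5.2% against 4.5% at 30% rates). On mid-p, the asymptotic test was at least as powerful in every case run and its level did not exceed 5.1%, so it remains the better choice. The subject-level responder wording is minor: the same paragraph speaks of lesions, so the intended unit is clear.

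**Conclusion.** The concern holds. The responder tests do not match the design, and the only method that would match it is optional. With positive correlation the chi-square does not inflate false positives. Its level falls to about 2–3% at phi 0.2 to 0.3, and for differences of 20 to 25 points from a 10% vehicle rate it gives up about 4 to 12 points of power against McNemar. At 60% versus 10% nothing material is lost.

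These sizes rest on an assumed phi, assumed smaller rates, 32 pairs, and an uncorrected pairwise reading of the chi-square. If the ITT analysis with carried-forward values includes up to about 36 pairs, the conclusion is the same. The mismatch itself is certain; the power loss in this trial is only plausible. The primary ANCOVA is untouched. This should be fixed, but it does not threaten the trial's main result.

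**What to change.** In section 9.1:

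- Define response per lesion (score 0).
- Make asymptotic McNemar without continuity correction the planned test of each concentration against vehicle, for PLA and SSA at Visits 5 and 9.
- Report a paired confidence interval for each difference in proportions, for example Newcombe or Agresti–Min.
- Do not substitute the exact or mid-p version, for the reasons shown in the working.
- Keep the repeated-measures logistic model, clustered on subject, as supportive. It could be the main method only with a small-sample variance correction and a stated rule for an arm with no responders.

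Align the statistical methods paragraph of the synopsis.

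The cost is protocol and SAP wording and a different procedure call on the same data. The one statistical price is about 4 points of power (66% against 70% at 35% versus 10%) if lesions within a subject are in fact independent.
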